5.5 Justification of the Inclusion and Exclusion Criteria

The eligibility criteria have been selected to enable evaluation of participants with and without Long-COVID in clearly defined, real-life, cohorts with previous SARS-CoV-2 infection. Additional eligibility criteria have been selected to enable evaluation of specific organ systems in the context of Long-COVID in selected sub-groups of the enrolled cohorts.

5.6 Participant Identification

All volunteers who provide informed consent to participate in the study will be allocated a unique sequential screening number which will be used as the primary identifier for the duration of the study for enrolled participants.

5.7 Co-enrolment Guidelines

Participants may be co-enrolled in other research studies if these are observational in nature or include behavioural interventions only. Other co-enrolments require approval by the Principal

Investigator after consideration of possible confounding effects and participant safety and well-being regarding blood draw volumes and exposure to multiple assessments.

6. STUDY VISITS

A brief screening assessment will be conducted for all study participants who provide informed consent for participation in the study. Those who are eligible for enrolment will continue into a baseline visit where all main study questionnaires will be administered, and assessments and procedures conducted.

Participants who are eligible for various sub-studies will be identified by the study team after review of their baseline visit results. Sub-study participants (up to 30 per cohort per sub-study) will be selected from these eligible participants and will be invited to provide separate informed consent for each sub-study. An additional visit or visits will be conducted for each sub-study. The number of study visits for each participant will depend on the number and type of sub-studies in which they participate. All study visits (including the screening/baseline visits and sub-study visits) will be completed for each participant within approximately 6 months.

Participants will be contacted telephonically within 28 days of the baseline visit, and again within 28 days of their last sub-study visit (if relevant) to inform them of the results of their assessments. For participants taking part in the overnight sleep study, however, feedback may be delayed until 6 months from the overnight visit. Abnormalities detected in assessments (suggesting undiagnosed medical, mental health, or sleep issues) will be managed by on-study medical personnel with referral as appropriate.

Questionnaires to be administered, and assessments and procedures to be conducted at each study visit (main and sub-studies) are detailed in Section 1. Details regarding each questionnaire, assessment and procedure are described in Section 7.

7. STUDY ASSESSMENTS, QUESTIONNAIRES, AND PROCEDURES

No study-specific assessments will be performed, or information gathered, until the potential participant has given written, informed consent (Section 11.2) for screening assessments and (if found to be eligible) for study participation.

The timing of all assessments and procedures is detailed in the Schedule of Assessments (Section **Error! Reference source not found.**).

7.1 Main Study

Screening and baseline assessments are expected to be performed on the same day but may be spread over two or more separate days given the expected duration of the visit (approximately 6 hours).

7.1.1 Screening assessments (Day 1)

SARS-CoV-2 infection and vaccination history will be collected. This will include:

- dates of positive SARS-CoV-2 PCR, antigen, and/or antibody tests
- dates of symptomatic COVID-19
- date and duration of hospitalisation for COVID-19 (if relevant)
- date(s) of COVID-19 vaccine(s) administration.

Review of the main study eligibility criteria will be performed for all participants providing informed consent for the main study (baseline visit). Participants may be re-screened if they may later become eligible for participation (due to, e.g., age or interval between SARS-CoV-2 infection and screening).

7.1.2 Baseline assessments, questionnaires, and procedures (Day 1 [+7 days])

The following main study (baseline) evaluations will be performed. These may be performed in any sequential order during the baseline visit. All questionnaires, surveys and rating scales will be administered in accordance with the specific guidelines associated with validated versions of the tools and will be included in the Study Assessments Manual.

Participants will be required to fast for 8 hours (water permitted *ad libitum*) prior to the drawing of blood for serum glucose assessments. If additional baseline assessments are scheduled for the same day as the blood draw, this will be performed as one of the first procedures of the visit and participants will be given a meal at the research unit before proceeding with the remaining assessments.

7.1.2.1 Demographics, social background and habits data

The following will be collected:

- Sex, age, race, and country of origin
- Town of residence
- Marital status, occupation, and educational attainment
- Socioeconomic status, access to healthcare, financial support, and debt
- Household conditions (including home type, water facility, toilet facility, assets), number of people in household, number of rooms in household used for sleeping, and number of people in household who have had COVID-19
- Use of tobacco products, alcohol, and illicit/street drugs.

7.1.2.2 Medical and surgical history

In addition to general information related to past and current relevant medical conditions and surgical procedures, and menstrual cycle, pregnancy and lactation status (for female participants only), the following specific information will be collected:

- COVID-19 history (for participants with previous symptomatic infection(s)) including:
 - Symptoms experienced (including cough, fatigue, fever, malaise, shortness of breath, ageusia, anosmia, and other symptoms)
 - Whether or not the participant was pregnant at the time of SARS-CoV-2 infection (female participants only)
 - Whether or not the participant required supplemental oxygen at the time of COVID-19
 - Whether or not the participant required intensive care unit (ICU) admission for COVID-19 (Cohort 3 only)
 - Whether or not the participant required mechanical ventilation for COVID-19 (Cohort 3 only)
- Long-COVID symptom-directed history to gather information about symptoms not assessed through the detailed questionnaires and surveys listed in Sections 7.1.2.5 to 7.1.2.6.

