- 2 Written or electronic informed consent to be provide prior to any screening or study-specific assessments, questionnaires or procedures are conducted.
- 3 Including dates of diagnosis through SARS-CoV-2 PCR or antigen testing, or date of positive antibody testing, COVID-19 vaccination dates (if administered), COVID-19 hospitalisation dates (if applicable).
- 4 Including information related to specific risk factors associated with poor COVID-19 outcomes and a detailed history of previous COVID-19 episodes (if applicable).
- 5 Targeting symptoms not covered in other administered surveys and questionnaires.
- 6 Details regarding previous and concomitant medications from the time of the participant's confirmed SARS-CoV-2 infection will be collected.
- 7 Including height and weight, and at least a general, cardiorespiratory, and skin examination and other systems as indicated through reported symptoms.
- 8 Vital signs (blood pressure, pulse rate, respiratory rate, body temperature, and SpO₂) will be measured after 5 min resting.
- 9 A standard 12-lead ECG will be conducted after the participant has rested in the supine position for 10 minutes.
- 10 A blood sample will be collected for full blood count, serum chemistry, liver function, renal function, glucose, HbA1C, and inflammatory markers assessments, and for DNA extraction for genotyping and sequencing.
- 11 Blood (50 mL) and urine (100 mL) samples will be stored for possible future analysis pending emerging information.
- 12 Study team personnel will review each participant's baseline data and identify participants with and without Long-COVID who are eligible for participation in one, or more, sub-study. Invited participants will be randomly selected from the set of eligible participants for each sub-study. Participants who decline the invitation to participate in one, or more, sub-study, will be replaced by a randomly selected, matched-cohort participant where possible.
- 13 Participants will be contact telephonically to inform them of the results of their baseline assessments, and to arrange for follow-up clinical consultations as required for any identified medical or mental health issues. Participants that have been selected for sub-study participation will be invited to return for consent and enrolment into these sub-studies.

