5.1 Cohorts

The following well-described cohorts of participants will be enrolled (approximately 100 participants in each):

- Cohort 1: participants who were asymptomatic but were found to be SARS-CoV-2 PCR/antigen/antibody-positive during routine screening previously

- Cohort 2: participants who were previous outpatients with symptomatic COVID-19 confirmed through a positive SARS-CoV-2 PCR/antigen test
- Cohort 3: participants who were previous inpatients and survived hospitalisation for severe COVID-19 confirmed through a positive SARS-CoV-2 PCR/antigen test
- Cohort 4: participants who were previously infected with SARS-CoV-2 (symptomatic or asymptomatic) confirmed through a positive PCR/antigen/antibody test after being vaccinated in a non-placebo arm of a SARS-CoV-2 vaccine trial in 2020, with a vaccine demonstrated to be effective against severe COVID-19.

Participants enrolled in early vaccine trials were screened out if they were concurrently infected with SARS-CoV-2 as detected through a minimum of PCR testing. Given that they were only exposed to the first wave of COVID-19 infections in South Africa during which severe lock-down measures were in place, the probability of them being infected with SARS-CoV-2 prior to vaccination would have been low.

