5.3.1 Inclusion criteria

1. Able and willing to provide written or electronic informed consent for the baseline visit prior to any study-specific assessment or procedure.
2. Age at least 18 years at the time of signing the informed consent form.
3. Previous asymptomatic SARS-CoV-2 infection, confirmed through a documented positive PCR, antigen, or antibody test, at least six months prior to the baseline visit **[Cohort 1 only]** or, previous symptomatic SARS-CoV-2 infection for which hospitalisation was not required, confirmed through a documented positive PCR or antigen test at the time, at least six months prior to the baseline visit **[Cohort 2 only]** or, previous hospitalisation for management and treatment of COVID-19 confirmed through a documented positive PCR or antigen test at the time, at least six months prior to the baseline visit **[Cohort 3 only]** or, previous asymptomatic or symptomatic SARS-CoV-2 infection, confirmed through a documented positive PCR, antigen, or antibody test, at least six months prior to the baseline visit and received a COVID-19 vaccine in a non-placebo arm of a COVID-19 vaccine study during 2020 **[Cohort 4 only]**.
4. Willing to consent to verification of vaccination status on the national Electronic Vaccination Data System (EVDS).
5. Access to a reliable telephone or other device permitting information transfer.

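### ICU admission and mechanical ventilation are asked of Cohort 3 only, so the top of the acute-severity scale is not recorded systematically for hospitalised Cohort 4 participants

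*Protocol*

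**What the plan says.** Protocol section 7.1.2.2 introduces the acute-illness history as "COVID-19 history (for participants with previous symptomatic infection(s)) including" a list of items. The heading applies to any cohort. One item, "Whether or not the participant required supplemental oxygen at the time of COVID-19", has no cohort limit. The next two do: "Whether or not the participant required intensive care unit (ICU) admission for COVID-19 (Cohort 3 only") and "Whether or not the participant required mechanical ventilation for COVID-19 (Cohort 3 only").

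Section 5.1 describes Cohort 4 as "participants who were previously infected with SARS-CoV-2 (symptomatic or asymptomatic) confirmed through a positive PCR/antigen/antibody test after being vaccinated" in a 2020 vaccine trial. The matching inclusion criterion in section 5.3.1 accepts "previous asymptomatic or symptomatic SARS-CoV-2 infection" and says nothing about hospital care. In that same criterion, Cohort 2 is confined to infections that did not need hospitalisation.

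At screening, section 7.1.1 collects "date and duration of hospitalisation for COVID-19 (if relevant") from all participants. Footnote 4 of the Schedule of Assessments (section 1) also calls for "a detailed history of previous COVID-19 episodes (if applicable"), without naming intensive care or ventilation.

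**The concern.** Limiting the two items to Cohort 3 makes sense only if every hospitalised participant is in Cohort 3. The eligibility criteria do not ensure that.

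The protocol gives its own reason for wanting the data. Section 2.1 warns that many Long-COVID symptoms resemble those of people hospitalised for any severe illness, and singles out patients who were in intensive care and ventilated. These two exposures are therefore a competing explanation for the symptoms that form the primary endpoint. Section 4.1 says the four cohorts will be compared and treats Cohort 4 as protected from severe disease. Section 9.2.2 plans to relate outcomes to COVID-19 history.

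If that history stops at a lower level in Cohort 4 than in Cohort 3, the two cohorts are not graded on the same scale at its upper end. A breakthrough case needing intensive care would also bear directly on the protection premise. Omitting the items because few such cases are expected would take the premise for granted.

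**Working it through.** No formula applies. The protocol states no sample size calculation (section 9.1) and gives no figure for hospitalisation in Cohort 4, so there is nothing to reproduce. The check sets eligibility against data collection.

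**Step 1: can a hospitalised person be in Cohort 4?**

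- Inclusion (5.3.1): asymptomatic or symptomatic infection at least six months earlier, plus active vaccination in a 2020 trial. There is no severity limit.
- Exclusion (5.3.2): the only criterion specific to Cohort 4 concerns infection before the trial vaccination.
- Cohort descriptions and recruitment (5.1, 5.2): the vaccine must have proved effective, but no limit is placed on the later infection.

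So yes. This follows from the absence of a restriction; the protocol does not say it outright.

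**Step 2: which acute-severity markers are specified in each cohort?**

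| Marker | Source | Cohort 3 | Cohort 4 |
|---|---|---|---|
| Dates of symptomatic illness | 7.1.1 | yes | yes |
| Acute symptoms | 7.1.2.2 | yes | yes, if symptomatic |
| Supplemental oxygen | 7.1.2.2 | yes | yes, if symptomatic |
| Hospitalisation, date and duration | 7.1.1 | yes | yes |
| ICU admission | 7.1.2.2 | yes | not required |
| Mechanical ventilation | 7.1.2.2 | yes | not required |

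**Step 3: what can be compared?** Asymptomatic, symptomatic without oxygen, oxygen, hospitalised, and length of stay can be compared across Cohorts 3 and 4. Within the hospitalised, Cohort 3 can be split by intensive care and ventilation; Cohort 4 cannot be split systematically.

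**Step 4: size.** The synopsis plans 100 participants per cohort, so each hospitalised Cohort 4 participant is 1/100 = 1 percentage point of a proportion in that cohort. How many there will be is unknown beforehand, but the screening data will show it. Only those among them who did receive intensive care or ventilation would be misplaced on the scale.

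**The case against.** The strongest reply is that little is lost. The protocol treats hospitalisation itself as the mark of severe disease: the primary objective equates severe symptoms with needing hospital care, and Cohort 3 is defined on that basis. Hospitalisation is recorded in every cohort. A reader might infer from the restriction that acute severity cannot be compared in Cohort 4, or that its protection from severe disease cannot be checked. The documents do not support either inference: both can be examined at the level of hospitalisation, with oxygen and length of stay as further detail.

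A reader might also infer that post-intensive-care effects in Cohort 4 would be wholly invisible. That goes too far. Intensive care for COVID-19 implies a hospital stay, so an analyst can describe the hospitalised members separately and so bound any such effect. The warning in section 2.1 covers hospitalisation for any severe illness, and that wider exposure is captured.

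Nor does the text show that the information will be absent for every such participant. The general history in Schedule footnote 4 may record some cases. A hospitalised vaccine-trial participant might also meet the Cohort 3 criteria, where both items are asked; no rule says which cohort takes precedence.

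Finally, the study is exploratory and no listed endpoint uses either item.

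These points stand and limit the finding, but they do not remove it. Footnote 4 names neither item while section 7.1.2.2 expressly confines both to Cohort 3, so capture elsewhere would be unsystematic. Setting aside all hospitalised participants bounds the effect of intensive care without separating it from that of hospitalisation. The protocol gives no reason for the restriction.

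**Conclusion.** The point holds in a limited form. ICU admission and mechanical ventilation are not required items for hospitalised Cohort 4 participants, although such people are eligible. The part of the severity scale above hospitalisation and oxygen therefore cannot be compared systematically between Cohorts 3 and 4. In Cohort 4, symptoms following intensive care cannot be separated from those following hospitalisation in general.

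This rests on reading the absence of a severity limit as permission to enrol hospitalised cases, and on the explicit cohort restriction governing what is asked. The number affected is not stated. It may be very small, or zero, if vaccination worked as the protocol presumes. No estimate of bias in the Long-COVID frequency can be drawn from the documents. This is a low-priority inconsistency in data collection. It cannot be left to the analysis plan, because an analysis cannot recover what was not asked at the baseline visit.

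**What to change.** In section 7.1.2.2, replace the Cohort 3 restriction on both items with: for any participant hospitalised for COVID-19, in any cohort. Open the two matching eCRF fields whenever a COVID-19 hospitalisation has been entered at screening.

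The cost is a short wording change and two yes/no questions for a few participants. It adds no procedure or sample and no burden for anyone who was not hospitalised. For participants already enrolled, the questions could be added to a follow-up telephone call if that contact is still to come.

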7.1.2.3 Previous and concomitant medications

Details of previous and ongoing medications taken from the time of the participant's confirmed SARS-CoV-2 infection will be collected.

7.1.2.4 Physical examination and vital signs

Height and weight (as measured in light indoor clothing or underwear only, but without shoes) will be measured, and body mass index (BMI) derived.

A symptom-directed physical examination will be performed (including at least a general, cardiorespiratory, and skin examination and other systems as indicated through reported symptoms).

Vital signs (blood pressure, pulse rate, respiratory rate, body temperature, and oxygen saturation [SpO_2]) will be measured after 5 min resting.

7.1.2.5 Psychological/psychosocial/sleep/work function evaluation

The following questionnaires/surveys will be administered to screen for general health and psychological issues:

- Psychological and Somatic Symptoms of COVID-19 Survey: a questionnaire assessing psychological symptoms of COVID-19 sequelae including fatigue, brain fog, headache, muscle weakness, delusions, hallucinations, disorganized thoughts/behaviours, slurred speech, and somatic symptoms
- Headache Impact Test-6 (HIT-6): a tool for assessing the impact of headaches in patients' day-to-day lives, including six main domains affected by headaches (pain, social functioning, role functioning, cognitive functioning, vitality, and psychological stress) [22]
- Patient Health Questionnaire-9 (PHQ-9): a multipurpose instrument for screening, diagnosing, monitoring, and measuring the severity of depression [23]
- Generalised Anxiety Disorder 7-item (GAD-7): a short screening tool evaluating 7 symptoms of anxiety in adults [24]
- PTSD Checklist – Civilian Version (PCL-C): a 20-item self-report measure that assessed the 20 DMS-5 symptoms of PTSD [25]
- Mood Disorder Questionnaire (MDQ): a short screening tool evaluating the symptoms of bipolar disorder [26]
- Montreal Cognitive Assessment (MOCA): a cognitive screening test designed to accurately and quickly assess short term memory, visuospatial abilities, executive functions, attention, concentration and working memory, language, and orientation to time and place [27]
- Daily Fatigue Impact Scale (D-FIS): a survey tool that assesses physical, cognitive, and psychosocial dimensions of fatigue in everyday life [28].

Psychosocial factors will be evaluated through the:

- COVID-19 Related Stress Survey: a survey assessing psychosocial stress experienced during the COVID-19 pandemic and lockdown [29]
- Multidimensional Scale of Perceived Social Support (MSPSS): a brief research tool designed to measure perceptions of support from 3 sources – family, friends, and a significant other; the scale is comprised of a total of 12 items, with 4 items for each subscale [30]

- Perceived Stress Scale-10 (PSS-10): a survey that assesses the degree to which situations in one's life are appraised as stressful; items are designed to query how unpredictable, uncontrollable, and overloaded respondents find their lives [31]
- Adverse Childhood Experiences (ACEs) Questionnaire: a short questionnaire assessing presence or absence of a pre-defined list of childhood traumas from the ages of 0 to 18 years [32].

Work performance in participants who are employed will be evaluated using the:

- Normal Activities and Work Productivity Questionnaire.

Sleep quality and associated disorders will be evaluated using the:

- Pittsburgh Sleep Quality Index (PSQI): a self-rated questionnaire which assesses sleep quality and disturbances over a 1-month time interval [33]
- Epworth Sleepiness Scale (ESS): a self-administered questionnaire consisting of 8 questions used to assess daytime sleepiness [34]
- Berlin Questionnaire: a self-administered questionnaire designed to identify subjects at high risk for obstructive sleep apnoea [35]
- International Restless Legs Syndrome Study Group Severity Rating Scale (IRLS) [36]
- Visual analogue scale: 10 cm lines with 2 anchors will be used to assess sleep quality and mood (best sleep ever had – worse sleep ever had; feeling happy and motivated, wanting to do things – feeling down and low, not wanting to do things).

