2. INTRODUCTION

2.1 Background

“Long-COVID” (also known as post-COVID-19 syndrome, post-acute sequelae of COVID-19, or chronic COVID syndrome, used here as ‘Long-COVID’ for brevity), is a complex array of postconvalescence symptoms following SARS-CoV-2 infection. The syndrome, common in COVID-19 survivors, can affect every organ system through as-yet uncharacterised but presumed immunological mechanisms. Prevalence depends on the definition used and time-period of follow-up, as well as the population being studied. The syndrome has been associated with significant and persistent disability in some survivors but has been hampered, until recently, by lack of a clinical definition, diagnostic criteria, and objective measures of disease or disability [1]. A Delphi-informed initial World Health Organisation (WHO) clinical definition was released in early October 2021 but has attracted much criticism from both clinicians and survivors for a host of reasons, ranging from a lack of precision to a lack of inclusion [2].

Further complicating the syndrome is the context in which the SARS-CoV-2 epidemic occurred, which was associated with severe lockdowns in many countries (including South Africa) with social isolation, widespread fear and disinformation, widespread economic hardship, and loss of family and acquaintances, all of which contribute to symptoms (psychiatric and sleep disturbances, pain, and other syndromes) reported to be associated with Long-COVID. Finally, many Long-COVID symptoms overlap with those seen in patients hospitalised for any severe illness, especially those admitted to intensive care and ventilated. However, the proliferation of literature reporting associations of Long-COVID symptoms with more severe COVID-19 disease, and objective immunological, radiological, and organ-specific dysfunction in those reporting symptoms, suggests that the entity is real. The pathogenesis of Long-COVID is poorly understood, but this association with more severe disease - where immune dysregulation plays a major role in those with hospitalization, respiratory failure, and death - suggests an immune-mediated inflammatory dysfunction that may impact all organs [3-14].

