3. OBJECTIVES AND ENDPOINTS

Primary	
Objectives	Endpoints
To characterise Long-COVID in four cohorts of patients with previous SARS-CoV-2 infection (asymptomatic, symptomatic, severely symptomatic requiring hospitalisation, and those who were vaccinated prior to widespread community exposure).	Incidence, severity, and duration of Long-COVID symptoms.
Secondary	
Objectives	Endpoints
To describe the following characteristics in four cohorts of patients with previous SARS-CoV-2 infection (asymptomatic, symptomatic, severely symptomatic requiring hospitalisation, and those who were vaccinated prior to widespread community exposure): 
• Inflammatory markers• Psychological profiles• Psychosocial exposures• Work performance in employed participants	
• High sensitivity C-reactive protein (hs-CRP)• Interleukin-1β (IL-1β)• Interleukin-6 (IL-6)• Interleukin-8 (IL-8)• Tumour necrosis factor alpha (TNFα)• Tumour necrosis factor alpha receptor-1 (TNFR1)• Monocyte chemoattractant protein-1 (MCP-1)• Headache Impact Test-6 (HIT-6)• Patient Health Questionnaire-9• Generalised Anxiety Disorder 7• PTSD Checklist for DSM-5 - Civilian Version• Mood Disorder Questionnaire• Montreal Cognitive Assessment• Daily Fatigue Impact Scale• COVID-19 related stress questionnaire• Multidimensional Scale of Perceived Social Support• Perceived Stress Scale• Adverse Childhood Experiences tool• Normal activities and work productivity questionnaire

• Sleep quality and disorders• Pain experience• Cardiorespiratory function• Standard laboratory parameters• Renal function• Host genetic factors that may be associated with Long-COVID	
• Pittsburgh Sleep Quality Index• Epworth Sleepiness Scale• Berlin Questionnaire for risk of sleep apnoea• International Restless Legs Syndrome Severity Scale• Sleep quality and mood visual analogue scale• Brief Pain Inventory• Modified Medical Research Council (mMRC) Dyspnoea Scale• Six-minute walk test (distance)• Electrocardiogram (ECG) parameters and morphology• Full blood count• Serum chemistry• Liver function tests• Glucose, glycosylated haemoglobin (HbA1C)• Creatinine clearance• Cystatin-C• Urine dipstick parameters• Urine albumin-to-creatinine ratio• Genotyping results• DNA sequencing results
Exploratory Objectives	

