After the baseline visit, participants with Long-COVID will be identified using the WHO clinical definition and general health assessments [2]. Randomly selected sub-groups of participants with, and without, Long-COVID will be selected from each of the four cohorts for additional investigations through participation in the following sub-studies:

- Respiratory evaluation: dyspnoea assessment, high-resolution computed tomography (CT) scan, lung function studies including spirometry and diffusion capacity (DLCO) [Section 7.2.2.1]
- Cardiac evaluation: clinical history and examination, serial blood pressure, six minute walk test (distance), ECG, echocardiogram including speckle tracking, cardiac magnetic resonance imaging (MRI), creatine kinase MB fraction (CK-MB), cardiac troponin T (cTnT), prohormone brain natriuretic peptide (pro-BNP), and possible coronary angiography in patients with acute coronary syndromes and unstable angina [Section 7.2.2.2]
- Psychiatric and neuroendocrine evaluation: questionnaires/surveys, semi-structured interview, home visit, saliva cortisol analysis, collection of diary data, actigraphy, adrenocorticotrophic hormone (ACTH) challenge (cosyntropin sensitivity test [CST]), cellular immunity assessment [Section 7.2.2.3]
- Sleep evaluation: questionnaires, actigraphy with sleep diaries, polysomnography (PSN) [Section 7.2.2.4]
- Pain evaluation: quantitative sensory testing (QST) and conditioned pain modulation (CPM) assessments [Section 7.2.2.5]
- Glucose metabolism evaluation: oral glucose tolerance test (OGTT) including assessment of glucose, insulin, and c-peptide to estimate insulin sensitivity and beta-cell function [16]. [Section 7.2.2.6]

Abnormalities detected in the assessments (including undiagnosed mental health issues) will be managed by on-study medical personnel with referral as appropriate.

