7.1.2.6 Pain assessment

Pain experience will be assessed using:

- The Brief Pain Inventory (BPI): a widely used questionnaire for the assessment of pain intensity, location, and interference with activities of daily living in clinical and research settings [37].

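### The Long-COVID symptom history is steered away from sleep, mood, anxiety and pain, and no described questionnaire dates their onset, so long-standing symptoms in these domains may be counted as Long-COVID.

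*Protocol*

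**What the plan says.** The primary endpoint in Protocol Section 3 is "Incidence, severity, and duration of Long-COVID symptoms". Under Section 4.1, status is assigned after the single baseline visit: "participants with Long-COVID will be identified using the WHO clinical definition and general health assessments".

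Sleep, mood, anxiety and pain are measured by the questionnaires in Sections 7.1.2.5 and 7.1.2.6. The Pittsburgh Sleep Quality Index is "a self-rated questionnaire which assesses sleep quality and disturbances over a 1-month time interval". The Brief Pain Inventory is "a widely used questionnaire for the assessment of pain intensity, location, and interference with activities of daily living". The PHQ-9 and GAD-7 belong to a group "administered to screen for general health and psychological issues".

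Section 7.1.2.2 also plans a "Long-COVID symptom-directed history to gather information about symptoms not assessed through the detailed questionnaires and surveys listed in Sections 7.1.2.5 to 7.1.2.6". Footnote 5 of the Schedule of Assessments (Section 1) repeats that limit. The same section takes a general history of relevant medical conditions, past and present.

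On other causes, Section 2.1 names lockdown isolation, fear, economic hardship and loss, "all of which contribute to symptoms (psychiatric and sleep disturbances, pain, and other syndromes) reported to be associated with Long-COVID".

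**The concern.** Incidence means that a symptom arose after infection. Duration means that its start is known. For sleep, mood, anxiety and pain, the protocol describes no item that supplies either fact, and it directs the one interview suited to asking for them toward other symptoms.

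These are among the domains that Section 4.1 calls a strong focus. Section 2.2 describes the diagnosis as one made by exclusion, and Section 2.1 says that the pandemic's social and economic effects contribute to the same symptoms. All four cohorts were infected, so no group shows the background frequency.

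If prior symptoms are counted, the frequency of Long-COVID may be overstated, and differences between cohorts may partly reflect differences in sleep, mental health and pain from before infection. Any error in status would carry into the sub-studies, which select participants with and without Long-COVID from the baseline data.

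**Working it through.** The protocol states no expected frequency, so there is no figure of its own to reproduce. The check is mainly a reading of the passages side by side.

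**1. What the endpoint needs.** Incidence and duration (Section 3) need, for each symptom, its status before infection and its date of onset.

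**2. What each source supplies, as described.**

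| Source | Section | Onset or pre-infection status for sleep, mood, anxiety, pain |
|---|---|---|
| Sleep index | 7.1.2.5 | One-month window; no onset described |
| Other sleep scales, PHQ-9, GAD-7 | 7.1.2.5 | None described |
| Brief Pain Inventory | 7.1.2.6 | Intensity, location, interference; no onset described |
| COVID-19 symptom survey | 7.1.2.5 | Framed as sequelae; names fatigue, brain fog, headache and somatic symptoms among others; timing not described |
| Symptom-directed history | 7.1.2.2; Section 1, footnote 5 | Limited to symptoms that the questionnaires leave out |
| General medical history | 7.1.2.2 | Known prior conditions may be recorded; no per-symptom onset |
| Medications | 7.1.2.3 | From confirmed infection onward, so treatment that ended earlier is not captured |

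**3. Reach of the sleep window.** Infection is at least 6 months before baseline (Section 5.3.1) and the window is 1 month. It therefore opens at least 6 − 1 = 5 months after infection and cannot show the pre-infection state.

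**4. Illustration of size.** The inputs are assumed, because the protocol gives neither. Let b be the share with the symptom before infection, and i the share of the rest who develop it afterwards. If every pre-existing symptom is counted and persists to the visit:

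- counted = b + (1 − b) × i
- share of those counted that predates infection = b / counted

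| b | i | Counted | Predates infection |
|---|---|---|---|
| 10% | 10% | 0.10 + 0.90 × 0.10 = 19% | 0.10 / 0.19 = 53% |
| 10% | 30% | 0.10 + 0.90 × 0.30 = 37% | 0.10 / 0.37 = 27% |
| 20% | 20% | 0.20 + 0.80 × 0.20 = 36% | 0.20 / 0.36 = 56% |
| 30% | 10% | 0.30 + 0.70 × 0.10 = 37% | 0.30 / 0.37 = 81% |
| 30% | 30% | 0.30 + 0.70 × 0.30 = 51% | 0.30 / 0.51 = 59% |

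**5. Set against sampling error.** Let p be the true proportion. If prior symptoms are independent of true Long-COVID and all are counted, the bias is (1 − p) × b. The 95% half-width for a cohort of 100 is 1.96 × √(p(1 − p)/100).

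| p | Half-width (points) | Bias at b = 10% | Bias at b = 20% |
|---|---|---|---|
| 10% | 5.9 | 9 | 18 |
| 30% | 9.0 | 7 | 14 |
| 50% | 9.8 | 5 | 10 |

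Under these assumptions, the bias would match or exceed sampling error once b is about 10% to 20%. All these figures are upper bounds, since the medical history and the case definition may remove some prior symptoms.

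**The case against.** Three points on the other side have force.

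- **Some pre-infection information is planned.** A reader might infer that nothing is recorded about symptoms before infection. The documents do not support that. The general history in Section 7.1.2.2 can record earlier depression, insomnia or chronic pain, and it is not limited to formal diagnoses. The COVID-19 symptom survey covers several other symptoms and is framed around sequelae. The gap is the lack of a systematic record of onset and prior status for each symptom.
- **The scales are secondary endpoints.** A reader might also infer that a poor sleep, mood or pain score makes a Long-COVID case. No section says so. Status rests on the WHO definition, whose criteria the protocol does not reproduce, and on general health assessments that it does not itemise. The psychological scales are introduced in similar terms, as general-health screening, so a link is plausible but not stated. Equally, no section says that pre-existing symptoms are removed.
- **The instruments are not shown in full.** Only the sleep index is described with a recall window, so the others cannot all be called current-state measures on this text. Section 7.1.2 places the tools in a Study Assessments Manual, and their items could narrow the gap.

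The SAP may add a counting rule, and the confounder list in Section 9.2.2 is open-ended. An analysis rule could use whatever the general history holds. It could not recover onset data that were never collected at a single visit.

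**Conclusion.** The point stands as a cheap improvement to data collection. A stated rule in Section 7.1.2.2 and footnote 5 keeps the symptom history away from sleep, mood, anxiety and pain, and no described questionnaire fills the gap. Long-standing symptoms in these domains may be counted as Long-COVID, and their duration since infection cannot be derived from the items described.

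The size is unknown. With b and i each assumed between 10% and 30%, the counted figure runs from 19% to 51%, and 27% to 81% of those counted predate infection. These are illustrations and upper bounds. They assume that every pre-existing symptom is counted and that none is removed by the history or the case definition. The documents do not show that Long-COVID frequency will be overstated, only that the plan as written does not guard against it in these domains.

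**What to change.** - **Lift the restriction.** In Section 7.1.2.2 and footnote 5, extend the symptom-directed history to sleep, mood, anxiety and pain. Do the same for headache, fatigue and cognition unless the COVID-19 symptom survey already records their onset.
- **Ask two items per symptom.** Was it present before the index infection (no; yes, unchanged; yes, worse since)? In which month did it begin? Infection and test dates are already collected under Section 7.1.1, so timing relative to infection follows directly.
- **State the counting rule.** Only new or worsened symptoms count toward the primary endpoint. Report the unrestricted figure alongside, so that no information is lost.

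The cost is a few minutes in a visit of about six hours, and some recall error about a period at least six months back.
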